COVER PAGE

Protocol #: STUDY 00002440

PROTOCOL TITLE

**Pilot Study of the Effect of Duavee® on Benign Breast Tissue Proliferation
in Peri or Post-Menopausal Women
at Moderate Risk for Development of Breast Cancer**

Principal Investigator: [name]
Protocol Chair University of Kansas Medical Center
[name]
[name]
[contact]
[contact]
[contact]

Co-Investigators: [name].
[name].

IND: **FDA IND Exempt (10 April 2015)**

Agent(s)/Supplier: Duavee® (Bazedoxifene/conjugated estrogens)
provided by Pfizer/Wyeth Pharmaceuticals, Inc.

Protocol Version:	Revision or Amendment #	Date	Approval
	Version 1.0c	24 June 2016	7 July 2016
	Version 1.0b	25 April 2016	4 May 2016
	Version 1.0a	4 March 2016	10 March 2016
	Version 1.0	6 July 2015	10 July 2015

SCHEMA

Pilot Study of the Effect of Duavee® on Benign Breast Tissue Proliferation
in Peri or Post-menopausal Women
at Moderate risk for Development of Breast Cancer

Population

Peri- or post-menopausal women ≤ 65 with a uterus and BMI < 36 kg/m² who are not taking systemic hormone replacement therapy, who exhibit vasomotor symptoms, and who are at moderate risk of developing breast cancer based on any of the following: 1st or 2nd degree relative with breast cancer, estimated mammographic breast density 25% or higher, prior biopsy showing proliferative breast disease, multiple prior biopsies, or by having either a 5-year risk Gail Risk (as calculated by the NCI Breast Cancer Risk Assessment Tool) or 10-year risk by the IBIS Breast Cancer Risk Evaluation Tool of 2X or more that of the average for the age group.

Women at very high risk such as those with a BRCA1/2 mutation or LCIS are **not** eligible.

Screening/Eligibility

Normal mammogram within 6 months of aspiration
If performed at KUMC, then eligible for optional volumetric (Volpara) and area (Cumulus) assessment of density
RPFNA yielding >500 cells on the Ki-67 and/or cytology slide;
Ki-67 $\leq 4\%$ positivity (500 or more cells)

Baseline Study Visit

Fasting blood draw to archive for serum SHBG, FSH, estradiol, testosterone, progesterone (progesterone for peri-menopausal only), chemistry profile, cytokine panel, and bazedoxifene levels. If peri-menopausal, negative pregnancy test required
DEXA Scan for bone density and body composition; Medical history and physical;
Height/weight
29 item validated Menopause Quality of Life Intervention Questionnaire and hot flash assessment

1. OBJECTIVES

Duavee® is tissue specific estrogen complex of bazedoxifene plus conjugated estrogen which is FDA approved for relief of menopausal symptoms and prevention of osteoporosis in women with a uterus who have not been diagnosed with estrogen dependent neoplasia. The overall purpose of this research is to demonstrate in a preliminary fashion that despite reduction in menopausal symptoms, (Duavee®) does not increase and may decrease proliferation in benign breast tissue in a cohort of peri- or post-menopausal women at moderately increased risk for breast cancer. If this pilot shows rapid accrual, good retention, and lack of significant increase in the risk biomarker Ki-67 in benign breast tissue, a larger prevention trial is envisioned in the Southwest Oncology Group

1.1 Primary Feasibility Objective

To determine feasibility for a larger clinical trial in women at moderately increased risk we will:

1.1.1 Determine if accrual is brisk as demonstrated by accrual of at least 20 moderate risk women in the initial 6 months (3.5 entrants per month) in a single institution;

1.1.2 Determine if there is a 15% or lower dropout rate over the 6 month intervention; and

1.1.3 Determine if 20% or fewer women with paired RPFNA specimens exhibit a meaningful increase in benign breast cell proliferation (Ki-67) where meaningful increase is defined as an increase in Ki-67 to 2% or higher in individuals with initial Ki-67 < 1% or a doubling of Ki-67 in individuals with initial Ki-67 of 1% or higher.

1.2 Secondary Exploratory Objectives

A number of analyses will be conducted in an effort to document and describe the effects of Duavee® on a variety of variables that are actual or potential risk biomarkers for development of breast cancer.

- Assess benign breast tissue for decrease in Ki-67 in women with Ki-67 of 1% or higher
- Assess changes in benign breast tissue estrogen responsive genes by RTqPCR
- Assess changes in benign breast tissue peptides and phosphopeptides.
- Assess changes in serum bioavailable hormones and cytokines
- Assess change in bazedoxifene serum levels as a function of BMI, percent body fat, and compliance (by tablet count)
- Document change if any in body composition (DEXA), and waist circumference
- Document change if any in volumetric breast density (Volpara) and compare to % dense area (Cumulus)

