5.2 Duavee® Administration

The KUMC Investigational Pharmacy will be responsible for receiving, inventory and dispensing of study agent.

A study number will be assigned to each participant and provided to the investigational pharmacy. Study agent will be dispensed with the study number and initials of each participant. Eight months of Duavee® will be dispensed. The study coordinator will then give the study agent to the participant with instructions to take one tablet at approximately the same time of day in conjunction with intake of food and to keep track of missed doses or lost tablets.

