6.2 Pharmacology

- 6.2.1 Absorption: Both bazedoxifene and conjugated estrogen are well absorbed from the gastrointestinal tract. Bio-availability of bazedoxifene is 6%. Steady state concentrations are obtained by day 10. At day 10 steady state C_{max} for the estrogen component is 2.6 ng/ml estrone and 6.9 ng/ml bazedoxifene with T_{max} after a single dose of 6.5 and 2.5 hours respectively in postmenopausal women.
- 6.2.2 Food Effect: Duavee® may be taken without regard to meals but a high fat meal increased the AUC by 25%.
- 6.2.3 Distribution: The estrogen component is bound to SHBG and albumin and is widely distributed. Bazedoxifene is also highly distributed and circulates highly bound (97-98%) to plasma proteins but not SHBG. A radio-ligand assay has been developed for bazedoxifene [Komm 2005 Endocrinology, Harris 2002]
- 6.2.4 Metabolism: The estrogen component is metabolized similarly to endogenous estrogen with conversion reversibly to estrone which can be converted to 17 B estradiol or estriol, or estrone sulfate. Bazedoxifene is metabolized via glucuronidation with little cytochrome P450 mediated metabolism. The concentration of the 5-glucuronidated metabolite in the circulation is 10x that of the parent compound.
- 6.2.5 Excretion: Total estrone is eliminated primarily in the urine with a half-life of 17 hours. Bazedoxifene is eliminated via biliary excretion and feces with <1% in urine. The elimination half-life of bazedoxifene is 30 hours. It is likely that it undergoes an extensive entero-hepatic circulation and that some drugs might interfere with elimination. However, commonly used antibiotics, NSAIDs, and antacids had minimal tested effect on Bazedoxifene concentrations with increases in AUC of Bazedoxifene of 6-7% with co-administration of ibuprofen, atorvastatin, and aluminum and magnesium hydroxide and decrease of bazedoxifene by 15% with azithromycin.

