6.5 Special Considerations

- 6.5.1 Hepatic or Renal Impairment: Duavee® is contraindicated in women with hepatic impairment (AUC of bazedoxifene increases by 100 % in moderate and over 300 % in severe hepatic impairment) and has not been evaluated in women with renal impairment. Women with significant hepatic or renal abnormalities will not be eligible for this study.
- 6.5.2 Women with high BMI: a 17% reduction in bazedoxifene is predicted in women with a BMI < 27 kg/m² compared those with > 27 kg/m². Reduction in bazedoxifene levels may be associated with increased risk of uterine hyperplasia in women using the Duavee® long term but it is unlikely to be an issue in our short term trial. Nonetheless we will restrict eligibility to women with a BMI of < 36 kg/m².
- 6.5.3 Advanced Age: No difference in safety or effectiveness were noted in the small number of women tested between 65-74 in clinical trials with Duavee® and Duavee® has not been tested in women over 75. Due to concerns about obtaining adequate amounts of breast tissue by RPFNA we will limit study entry to those 65 and younger.

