Secondary to analysis of Ki-67, other variables will be assessed that represent a wide variety of cellular, molecular, and physical factors that have been proposed to have some level of connection with the process of breast cancer development. Categorized by the “specimen” being assessed, the variables are:

Participant

- Mammographic breast density
- Weight and BMI,
- DEXA body composition and waist measurement

Blood

- Hormones
- Adipocytokines
- Bazedoxifene levels

RPFNA

- Cytomorphology (categorical)
- Peptides and phosphopeptides (proteomics)
- Gene expression (RT-qPCR)

Descriptive statistics will be used to summarize the values at baseline (prior to start of intervention), at 6 months (after completion of intervention), and the change (both absolute and relative) from baseline to off-study. Medians, ranges, and interquartile ranges will be employed for all variables, along with mean and standard deviation for variables shown to be normally distributed. As appropriate, 95% confidence intervals will also be computed.

It should be noted that these variables are anticipated to be assessed for all participants that provide paired specimens, and thus the total should be close to 40. This provides additional opportunity to achieve normal distributes and to conduct exploratory correlational analyses. Thus paired t-test will be used for normally distributed values (initial or after appropriate transform), but nonparametric tests such as the Wilcoxon signed rank test will be used when necessary

Since these analyses are considered as exploratory, no adjustments will be made for multiple comparisons and $p < 0.05$ will be considered the criterion for statistical significance. However, caution will be employed in the interpretation and presentation of the results.

Lastly, an assessment of menopause symptom relief in this cohort will be conducted using a 29 item validated Menopause Quality of Life Intervention Questionnaire and hot flash assessment. The same statistical methods as above will be employed. The intent is not statistically significant “proof” of efficacy as Duavee® is already FDA-approved for this indication.

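### Bazedoxifene level is analysed as change from a baseline that should be zero, with no term for time since the last tablet

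*Combined protocol and SAP*

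**What the plan says.** Section 1.2 lists the exploratory objective "Assess change in bazedoxifene serum levels as a function of BMI, percent body fat, and compliance (by tablet count"). Section 13.4 places bazedoxifene levels in a mixed list of blood, tissue and physical variables. All of them are to be summarised at baseline, at 6 months and as "the change (both absolute and relative) from baseline to off-study", with a paired t-test or signed-rank test.

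On timing, Section 5.2 tells each woman to "take one tablet at approximately the same time of day in conjunction with intake of food". This steadies the hour within a woman but leaves it free between women. Section 7.2.3.3 asks for a 10–12 h fast. Section 7.4 puts the end-of-study draw before the aspiration, on the same day where possible. Section 13.5 measures compliance by a tablet count at the end of treatment. Its only rule on recency of dosing is a last dose within 2 weeks of the aspiration, and that applies to supporting analyses alone.

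On pharmacology, Section 6.2 states "The elimination half-life of bazedoxifene is 30 hours" and "Steady state concentrations are obtained by day 10". Section 6.5.2 states "a 17% reduction in bazedoxifene is predicted in women with a BMI < 27 kg/m² compared those with > 27 kg/m²".

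**The concern.** Two features of the analysis do not suit this analyte.

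First, the baseline draw comes before any study tablet. Section 4.2.3 excludes systemic hormones within 8 weeks before screening and any chemoprevention trial within 6 months. Section 4.4.2 excludes hormone replacement started between aspiration and enrolment. Baseline bazedoxifene should therefore be zero or below quantification, and the plan gives no rule for such values. A ratio to that baseline has no meaning.

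Second, the end-of-study level is one spot sample of a drug that falls between tablets. A woman who takes her tablet with an evening meal is drawn roughly 12 h later. One who takes it with breakfast, after the fasting draw, is drawn roughly 24 h after the previous tablet. The stated analysis has no term for this difference. Tablet count is cumulative and cannot show when the last tablet was taken.

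At stake is how well the trial can describe the relation of level to BMI, body fat and compliance. A dosing hour not noted at the draw is hard to recover later.

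**Working it through.** **Inputs from the documents.** Half-life 30 h, steady state by day 10 and bazedoxifene Tmax 2.5 h (Section 6.2). BMI effect 17% (Section 6.5.2). Fast of 10–12 h (Section 7.2.3.3). 36 evaluable women (Section 3).

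**Assumptions, because the documents give no figure.** Between-woman residual SD of log level 0.15 to 0.40. Dosing hours either an even split at 12 h and 24 h, or uniform from 12 h to 24 h. Two BMI groups of 18. Single-exponential decline after the peak.

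**Check of the plan's own figures.** The 17% is a quoted prediction without inputs and cannot be reproduced. Steady state by day 10 agrees with the half-life: 240/30 = 8 half-lives, and 1 − 2^(−8) = 99.6%.

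**Baseline.** Eight weeks is 56 × 24/30 = 44.8 half-lives, so nothing measurable would remain from any use before that window. Absolute change = end-of-study level − 0 = end-of-study level. Relative change = level/0, which is undefined.

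**Size of the timing effect.** The fraction remaining after t hours is 2^(−t/30).
- Time to fall 17%: 30 × log2(1/0.83) = 8.1 h. If the half-life were 20 to 40 h, this would be 5.4 to 10.8 h.
- 24 h against 12 h after a tablet: 1 − 2^(−12/30) = 24% lower.
- Last tablet missed, a further 24 h: 1 − 2^(−24/30) = 43% lower.
- A difference of only 4 h: 1 − 2^(−4/30) = 9% lower.
- At the 2-week limit of Section 13.5: 336/30 = 11.2 half-lives, so 0.04% remains. That rule does not control sampling time.

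**On the log scale.** The BMI effect is −ln(0.83) = 0.186. The decline per hour is ln 2/30 = 0.0231. Timing SD is 0.0231 × 6 = 0.139 for the even 12 h/24 h split, and 0.0231 × 12/√12 = 0.080 for uniform 12–24 h.

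**Power to detect the 17% effect** (simulated least-squares regression of log level, two-sided 0.05, dosing hour independent of BMI), without → with a term for hours since tablet:

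| Residual log SD | Even 12 h/24 h split | Uniform 12–24 h |
|---|---|---|
| 0.15 | 76% → 95% | 88% → 94% |
| 0.20 | 61% → 77% | 71% → 77% |
| 0.30 | 38% → 44% | 42% → 44% |
| 0.40 | 25% → 27% | 26% → 27% |

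Reruns differ by about 1 point.

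**Hand check of the first cell.** Without the term, the SD is √(0.15² + 0.139²) = 0.2045 and the standard error is 0.2045 × √(2/18) = 0.068. Then 0.186/0.068 = 2.73, and power is about Φ(2.73 − 1.96) = 78%. With the term, the standard error is 0.15/3 = 0.05, the ratio is 3.73 and power is about Φ(1.77) = 96%. Both agree with the simulation to within the normal approximation.

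**The case against.** The strongest reply is that this matters little. The objective is exploratory, Section 13.4 says the study is not powered for biomarker change, and results are to be read with caution. That stands, and it caps the importance of the point.

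Absolute change is also sound. With a zero baseline it already is the outcome one would want, so only the relative-change summary and the paired test fail. They come from a sentence written for a mixed list of variables. That stands too; a reader might infer that the whole analysis of change is invalid, and it is not.

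A reader might also infer that timing distorts the BMI relation. It does so only if dosing hour is associated with BMI, body fat or compliance, and the documents give no reason to expect that. Otherwise the cost is precision.

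Nor do the documents show that timing generally outweighs BMI. They give no distribution of dosing hours. If the fast and the with-food instruction are both followed, the interval runs from about 10–12 h to 24 h, and a uniform 12–24 h spread has a log SD of 0.080, less than half of 0.186. The 43% figure cannot arise between two women who both take a tablet daily; it needs a missed last tablet. Section 5.2 asks women to track missed doses, so compliance may absorb part of that.

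Finally, the comparator is soft. The 17% has no stated metric, and Section 6.2 thinks extensive entero-hepatic circulation likely, so single-exponential decline is an approximation. The case report form is not among the documents, and the 2-week rule implies that a last-dose date is known. What remains is that no section asks for a clock time, limits the interval or includes it in the analysis.

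**Conclusion.** The point holds as a minor improvement. Relative change and the paired test are uninformative for bazedoxifene, given a baseline inferred to be zero from the exclusions, which do not name bazedoxifene. Time since last tablet is an omitted covariate. An 8.1 h difference in sampling time equals the whole quoted BMI effect, and the plausible 12 h to 24 h range exceeds it at 24%.

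The gain from adjustment depends on quantities that the documents do not give. It is about 19 points of power with an even 12 h/24 h split and residual log SD 0.15, about 6 points with uniform timing at the same SD, and no more than about 2 points at SD 0.40. These figures assume 36 women in two equal BMI groups, and dosing hour unrelated to BMI.

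A reader might go further and conclude that a feasibility, Ki-67 or safety finding is weakened. None of these uses bazedoxifene levels.

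The direction of the 17% must also be reconciled: the printed sentence puts the reduction below a BMI of 27, under a heading on high BMI. The size used here does not depend on the direction.

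**What to change.** 1. Record the date and clock time of the last tablet and of the end-of-study draw.
2. Regress the log end-of-study level on BMI or percent body fat, tablet-count compliance and hours since last tablet.
3. For this analyte, drop relative change and the paired test, and report the end-of-study level.
4. State how values below quantification are handled, both at baseline and on the log scale at the end of study.
5. Reconcile the direction of the BMI statement in Section 6.5.2 with its heading.

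The cost is one or two case report form fields and one degree of freedom. No visit, procedure or dosing instruction changes.

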2. BACKGROUND

2.1 The Scope of the Problem

Vasomotor and other menopausal symptoms are a significant problem impacting quality of life for up to 75% of women undergoing natural menopause transition usually between age 45 and 55 and generally last about 5 years [Freeman, 2011]. Approximately 1/3 of women have severe enough symptoms to prompt them to seek medical attention. These women and those who develop vasomotor symptoms early in transition are likely to be those who are bothered with these symptoms for 10 or more years [Freeman, 2011; Freeman, 2014]. Hormone replacement therapy, either estrogen alone for women without a uterus or estrogen and progesterone for women with a uterus, is the most effective means of relief but concerns about increasing the risk for breast cancer make providers reluctant to provide prescriptions for hormone replacement therapy for even average risk women much less those at increased risk. Reluctance is largely based on results of the Women's Health Initiative study in which an average of 5 years of combined conjugated estrogen 0.625 mg plus a progestin resulted in a 24% increase in breast cancer risk overall and a 34% increase in risk for women beginning it in their 50's (HR 1.34; 0.82-2.19) [Manson 2013; Anderson 2012]. No increase in risk of breast cancer was observed for conjugated estrogen 0.625 mg/day alone [Manson 2013; Anderson 2012].

At least 25% of women 45 and older are at increased risk for breast cancer because of family, reproductive, or personal health history. In addition to counseling for lifestyle modifications (normal weight, exercise, reduce alcohol intake), peri- and post-menopausal women 35 and older at moderately or higher increased risk may be counseled to take an anti-estrogen to reduce their risk [Visvanathan 2013]. Overall only 4% of women eligible for antihormonal primary prevention therapy agree to take it although it can reduce the risk of breast cancer by 40% or more [Fisher 1998; Vogel 2006; Ropka 2010; Goss 2011; Cuzick 2013; Cuzick 2014].

Given that medications such as tamoxifen and aromatase inhibitors often increase vasomotor symptoms and are not associated with a survival advantage in the primary prevention setting [Visvanathan 2013; Goss 2011; Cuzick 2014], it is likely that an even lower percentage of women currently having difficulty with hot-flashes will agree to take anti-estrogens as primary prevention therapy. The development of tissue selective estrogen complexes combining estrogen (for hot flashes and bone health) plus a selective estrogen receptor modulator (SERM) with breast and uterine antagonist activity presents a potential solution to this conundrum for women with both vasomotor symptoms and an increased risk for development of breast cancer.

2.2 Rationale for Present Proposal

In clinical trials of bazedoxifene plus conjugated estrogen (now marketed as Duavee®) versus placebo, relief of hot flashes and improvement of both hip and lumbar spine bone density was accomplished without development of uterine hyperplasia, increase in breast tenderness, or increase in mammographic breast density [Harvey 2013; Pinkerton 2013; Pinkerton 2014a; Pinkerton 2014b; Pinkerton 2014c; Abraham 2014; Komm 2014]. Contra-indications to use of Duavee® include estrogen dependent neoplasia (such as breast, ovarian, and endometrial cancer), predisposition to or prior thromboembolism, hepatic impairment, and abnormal uterine bleeding. There is no explicit label warning about women who may be at increased risk for breast cancer [Duavee® Prescribing Information, 2014].

Preclinical studies in MCF-7 breast cancer cells suggests that bazedoxifene down-regulates ER alpha and decreases cyclin D1 as well as cell growth [Lewis-Wambi 2011].

In non-human primates, 6 months of bazedoxifene or bazedoxifene combined with conjugated estrogen was associated with reduced Ki-67 compared to conjugated estrogens alone in normal mammary tissue [Ethun 2012]. Bazedoxifene combined with conjugated estrogen still functions as an estrogen antagonist in the macaque monkey uterus with reduction of Estrogen Receptor alpha (ER alpha) related genes GREB1 and pS2 (Trefoil Factor 1) [Ethun 2013]. There was little effect on lipids or coronary or peripheral atherosclerosis for bazedoxifene alone but bazedoxifene partially antagonized the protective effects of conjugated estrogens on coronary and peripheral but not cerebral/carotid atherosclerosis [Clarkson 2014].

There is no FDA approved chemopreventive agent for breast cancer risk reduction which reduces menopause symptoms, in fact the SERMs tamoxifen (for pre and postmenopausal women) and raloxifene (for postmenopausal women), as well as aromatase inhibitors (for postmenopausal women), all increase menopause symptoms [Visvanathan 2013]. If bazedoxifene and conjugated estrogens were actually found to reduce proliferation in benign breast tissue similar to what has been observed in animal models, then it should be explored in placebo-controlled Phase IIB trials for change in tissue proliferation and in Phase III trials for change in cancer incidence. The combination of menopause symptom relief and breast cancer risk reduction would be a major advance for women in early menopause. Even if breast cell proliferation did not decrease but was at least stable (not increased) after Duavee®, this would be a major advance as women at increased risk for breast cancer (and their physicians) would likely be more comfortable with its use.

